12.8 Interim Analysis

The total expected number of deaths is 22 at the end of the follow-up period. A single interim analysis is planned after 14 deaths occur. The purpose of this analysis is to allow an early assessment of efficacy. We shall use a Hwang-Shih-DeCani group-sequential boundary with $\gamma = -4$, yielding an O'Brien-Fleming-like α spending function and a one-sided stopping boundary (30). We expect to spend approximately 0.0052 of the total of $\alpha = 0.025$ at the interim analysis and the remaining 0.0198 at the final analysis. Thus the p-value in the interim must be less 0.0052 to conclude that the two arms are significantly different. At the final analysis the p-value would need to be less than 0.0198 for the two arms to be significantly different.

Power calculations were carried out using Version 1.0 the “gsDesign” package in the R statistical system (R language and environment for statistical computing, R Foundation, Vienna, Austria).

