	
doses > 10 mg daily prednisone equivalent, are permitted in the absence of active autoimmune disease.
 
11. Participants with history of life-threatening toxicity related to prior immune therapy (e.g. anti-CTLA-4 or anti-PD-1/PD-L1 treatment or any other antibody or drug specifically targeting T-cell co-stimulation or immune checkpoint pathways) except those that are unlikely to reoccur with standard countermeasures (e.g. Hormone replacement after adrenal crisis)
 
12. Patients with serious or uncontrolled medical disorders.
 
13. Treatment with botanical preparations (e.g. herbal supplements or traditional Chinese medicines) intended for general health support or to treat the disease under study within 2 weeks prior to randomization/treatment.
 
14. History of allergy or hypersensitivity to study drug components.
 
15. Has received a live vaccine within 30 days of the planned start of study therapy. Note: seasonal flu vaccines for injection are generally inactivated vaccines and are allowed, however intranasal influenza vaccines are live attenuated vaccines and are not allowed.
 
16. History of allogenic stem cell or solid organ transplant.

STATISTICAL CONSIDERATIONS	
This is a phase II randomized (1:1) clinical trial comparing the control group receiving standard of care perioperative chemotherapy, nivolumab and surgery to the experimental group receiving perioperative chemotherapy, nivolumab in combination with the CV-301 vaccine.
 
Based on a study by Morse et al.¹, the survival probability of the control group at 3 years is 0.588. With a sample size of 70 resected patients (35 per study arm), we will have 80% power to detect an increase in the 3-year OS rate from 58.8% to 88.7% using a 2.5% level one-sided log-rank test. Note that the 3-year survival rate of the vaccine treated cohort in the study by Morse et. al. was 92.5%. We will enroll 74 patients, with the expectation that about 5% of the patients will not go on to resection due to either disease progression or complications of neoadjuvant therapy [2], leaving us with approximately 70 resectable patients. If the number of unresectable patients is higher than 5%, then we will enroll up to 78 patients.
 
An analysis is planned at 2.5 years. The purpose of this analysis is allow an early assessment of efficacy.

TOTAL NUMBER OF SUBJECTS	N = 78 patients
ESTIMATED ENROLLMENT PERIOD	Estimated 12 months

ESTIMATED STUDY DURATION	Estimated 60 months

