12.3 Sample Size and Accrual

This is a 1:1 randomized clinical trial comparing CV-301 vaccine to standard treatment in patients with resectable hepatic metastatic colorectal cancer. Based on a study by Morse et al. [17], the OS probability at 3 years is 0.588. We would like to detect an increase in OS in the CV-301 study arm with 80% power, using a 2.5% level one-sided log-rank test. This survival analysis will be from the time of metastasectomy.

With a sample size of 70 resected patients (35 per study arm), we will have 80% power to detect an increase in the 3-year OS rate from 58.8% to 88.7% using a 2.5% level one-sided log-rank test. Note that the 3-year survival rate of the vaccine treated cohort in the study by Morse et. al. was 92.5%. We will enroll 74 patients, with the expectation that about 5% of the patients will not go on to resection due to either disease progression or complications of neoadjuvant therapy³, leaving us with approximately 70 resectable patients. If the number of unresectable patients is higher than 5%, then we will enroll up to 78 patients.

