12.7 Data Analysis Plan

A 2.5% one-sided log-rank test will be used to test the primary hypothesis. The estimation of recurrence free survival and OS will be performed by the Kaplan-Meier product limit method on all patients who undergo complete resection. Descriptive statistics for all outcome measures will be provided. To evaluate the association between variables, either chi-square test (categorical vs. categorical) or two sample t-test (categorical vs. continuous) or correlation (continuous vs.

continuous) will be used depending upon the types of variables in comparison.

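### The final cut-off of p < 0.0198 is the alpha left to spend, not the nominal boundary (about 0.0232), so the written rule runs at about 2.17% one-sided instead of 2.5%

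*Combined protocol and SAP*

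**What the plan says.** Section 12.3 sizes the trial to detect an increase in 3-year overall survival from 58.8% to 88.7% in 35 resected patients per arm, "with 80% power, using a 2.5% level one-sided log-rank test". Section 12.7 repeats the level: "A 2.5% one-sided log-rank test will be used to test the primary hypothesis".

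Section 12.8 adds the group-sequential rule. On the final count: "The total expected number of deaths is 22 at the end of the follow-up period". On the interim: "A single interim analysis is planned after 14 deaths occur". The boundary is named: "We shall use a Hwang-Shih-DeCani group-sequential boundary with" gamma = -4, with a one-sided stopping boundary, and the calculations are attributed to the gsDesign package. About 0.0052 of the 0.025 is to be spent "at the interim analysis and the remaining 0.0198 at the final analysis". The same two numbers then become the decision rule: p below 0.0052 at the interim, and "At the final analysis the p-value would need to be less than 0.0198 for the two arms to be significantly different".

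The synopsis (Statistical Considerations) describes the early look by calendar time instead: "An analysis is planned at 2.5 years". No other section gives a nominal final boundary, or a rule for recomputing the boundaries if the death counts differ.

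**The concern.** An alpha increment and a nominal p-value boundary are the same number only at the first look. At the second look, part of the probability of exceeding any cut-off belongs to trials that already crossed at the interim. The increment spent is therefore smaller than the nominal p. Using the increment as the cut-off treats the looks as if their error rates simply added up, and leaves some of the 0.025 unused.

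This is the success rule for the primary endpoint. With a final p of, say, 0.022, the number in 12.8 says negative, while the named spending function says positive. So does 12.7 read alone, because it states 2.5% without pointing to 12.8. That ambiguity should be removed before survival data are seen.

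The cut-offs are also fixed numbers, although both boundaries depend on the death count at the early look, and the synopsis and 12.8 give different triggers for it.

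**Working it through.** **Inputs.** Overall one-sided alpha 0.025 (12.3, 12.7, 12.8); interim at 14 deaths, 22 expected in total, Hwang-Shih-DeCani with gamma = -4, cut-offs 0.0052 and 0.0198 (all 12.8); 3-year survival 58.8% vs 88.7%, 35 per arm (12.3).

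**1. The plan's figure.** 0.025 - 0.0052 = 0.0198. The stated cut-off is exactly the remaining alpha.

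**2. Interim spend.** The spending function is alpha(t) = 0.025 × (1 - exp(4t)) / (1 - exp(4)). At t = 14/22 = 0.636, exp(4t) = 12.749 and exp(4) = 54.598, so alpha(t) = 0.025 × 11.749 / 53.598 = 0.00548. At t = 0.625 it is 0.00522. A spend of 0.0052 needs t = 0.624, that is, 14 of about 22.4 deaths. The plan says approximately, so an unrounded total would explain the difference.

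**3. Level of the written rule.** Under the null, the two statistics are bivariate normal with correlation sqrt(14/22) = 0.80. The cut-offs are z = 2.562 (p = 0.0052) and z = 2.058 (p = 0.0198). Then 1 - P(Z1 < 2.562, Z2 < 2.058) = 0.02167. The final look spends 0.02167 - 0.0052 = 0.0165, not 0.0198. A simulation of 20 million draws gives 0.02168.

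**4. Boundary of the named design.** Solve P(Z1 < c1, Z2 > c2) = remaining alpha for c2.

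| Interim p | Remaining alpha | c2 | Nominal final p |
|---|---|---|---|
| 0.00548 (exact spend at 14/22) | 0.01952 | 1.992 | 0.0232 |
| 0.0052 (as written) | 0.0198 | 1.989 | 0.0233 |

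Under the null, the outcome turns on the gap from 0.0198 to 0.0232 in about 0.32% of trials.

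**5. Power.** Under proportional hazards, HR = ln 0.887 / ln 0.588 = 0.226. With 22 deaths:

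| Method | Written rule | 0.0055 / 0.0232 |
|---|---|---|
| Freedman-type drift, sqrt(22) × (1 - HR)/(1 + HR) = 2.96 | 82.1% | 83.8% |
| Schoenfeld-type drift, sqrt(22/4) × abs(ln HR) = 3.49 | 92.6% | 93.5% |
| Log-rank simulation, 200,000 runs | 88.7% | 90.5% |

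**6. Other death counts.** With the interim at 14 deaths and the spend recomputed, the nominal final p is 0.0223 for 18 final deaths, 0.0228 for 20, 0.0232 for 22, 0.0236 for 26 and 0.0240 for 32. It is always above 0.0198.

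If the early look is timed at 2.5 years instead, exponential survival at the plan's rates gives about 13.1 deaths, taking 2.5 calendar years from the first resection with uniform entry over 12 months. It gives about 15.8 if every patient has 2.5 years after resection. Both readings are assumptions, because the synopsis does not say when its 2.5 years start. From 13 to 16 of 22 deaths, the interim boundary moves from 0.0045 to 0.0081 and the final boundary from 0.0234 to 0.0227. The fixed rule 0.0052/0.0198 would run at 2.19% to 2.11%.

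**7. Small-sample check.** Null log-rank simulations with 35 per arm and looks at deaths 14 and 22 give 0.0210 to 0.0218 for the written rule and 0.0249 to 0.0260 for 0.0055/0.0232. The run at the top of both ranges had 400,000 replicates, with standard errors of 0.0002 and 0.0003.

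**The case against.** The strongest reply is that nothing promised to patients or regulators is broken. The rule keeps type I error below 2.5%. On the plan's own effect with 22 deaths, its power exceeds the stated 80% by all three methods, and the null decision changes in about 1 trial in 300. A cut-off of 0.0198 would be legitimate if it were described as deliberately conservative. All of that stands, and it limits the seriousness of the point. It does not remove the error, because 12.8 derives 0.0198 as the remainder of 0.025 and presents the rule as using the full level.

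A second reply is that 0.0232 is a large-sample boundary applied to about 22 deaths, and one simulation puts its actual size at 0.0260. This is fair. The excess is marginal, and another run gives 0.0249, but the replacement boundary should come with a check of its size. It is no defence of 0.0198, which was obtained by subtraction and not as a small-sample correction.

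Two further points also have weight. The gap between 0.0052 and 0.0055 is within the plan's own approximation and matters only as a reason to recompute at the actual counts. The conflict over the early-look trigger is separate from the arithmetic, but it bears on the same boundaries and can be settled in the same edit.

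**Conclusion.** The concern holds. Section 12.8 uses remaining alpha as a nominal p-value threshold. For 14 of 22 deaths, the written rule has an overall one-sided level of 0.0217 rather than 0.025, and the named design's final boundary is 0.0232 (0.0233 if the interim cut-off stays at 0.0052). The error is conservative and costs about 1 to 2 points of power. It should be fixed because it is the primary decision rule and a p-value in the gap would be open to dispute.

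The levels and boundaries rest on the large-sample joint normality of the log-rank statistics, with information proportional to deaths. The power figures also assume proportional hazards and 22 deaths at the final analysis.

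**What to change.** - **Section 12.8, increments.** Label the two figures as alpha increments: 0.0055 and 0.0195 at 14 of 22 deaths.
- **Section 12.8, boundaries.** Give the nominal boundaries as p < 0.0055 at the interim and p < 0.0232 (z > 1.992) at the final analysis for 14 of 22 deaths, both recomputed from the spending function at the actual death counts. If the interim cut-off is kept at 0.0052, the matching final boundary is p < 0.0233 (z > 1.989). If the sponsor prefers to keep 0.0198, the text should say that the choice is conservative and does not use the full 2.5%.
- **Small-sample size.** State whether a permutation log-rank p-value will be used, or report the simulated size of the adopted boundaries with about 22 deaths.
- **Section 12.7.** State that 2.5% is the overall one-sided level and refer to 12.8 for the boundary at each look.
- **Synopsis and 12.8.** Use one trigger for the early look. If it is calendar time, define its starting point.

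The cost is a few sentences in 12.7, 12.8 and the synopsis. No extra patients or data are needed.

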13. TRIAL MANAGEMENT

13.1 Data and Safety Monitoring Plan (DSMP)

The study will be conducted with guidance from the Rutgers Cancer Institute of New Jersey's DSMP.

HCRN oversight activities include:

- Review and processing all adverse events requiring expedited reporting as defined in the protocol
- Provide trial accrual progress, safety information and data summary reports to the sponsor-investigator
- Submit data summary reports to the lead institution Data Safety Monitoring Committee with guidance from Rutgers Cancer Institute of New Jersey's DSMP.

13.2 Rutgers Cancer Institute of New Jersey's Data Safety Monitoring Committee

HCRN will provide the following for review:

- Adverse event summary report
- Audit results if applicable
- Data related to stopping/decision rules described in study design
- Study accrual patterns
- Protocol deviations

The Rutgers Cancer Institute of New Jersey's DSMC will review study data on a quarterly basis. Documentation of DSMC reviews will be provided to sponsor-investigator and HCRN. Issues of immediate concern by the DSMC will be brought to the attention of the sponsor-investigator and other regulatory bodies as appropriate. The sponsor-investigator will work with HCRN to address the DSMC's concerns.

13.3 Data Quality Oversight Activities

Remote validation of the EDC system data will be completed on a continual basis throughout the life cycle of the study. Automated edit check listings will be used to generate queries in the EDC system and transmitted to the site to address in a timely fashion. Corrections will be made by the study site personnel.

Monitoring visits to the trial sites may be made periodically during the trial to ensure key aspects of the protocol are followed. For cause visits may occur as necessary. Source documents will be reviewed for verification of agreement with data entered into the EDC system. It is important for the site investigator and their relevant personnel to be available for a sufficient amount of time during the monitoring visits or audit, if applicable. The site investigator and institution guarantee access to source documents by HCRN or its designee.

The trial site may also be subject to quality assurance audit by Bavarian Nordic, BMS or its designee as well as inspection by appropriate regulatory agencies.

13.4 Compliance with Trial Registration and Results Posting Requirements

Under the terms of the Food and Drug Administration Modernization Act (FDAMA) and the Food and Drug Administration Amendments Act (FDAAA), the sponsor-investigator of the trial is solely responsible for determining whether the trial and its results are subject to the requirements for submission to the Clinical Trials Data Bank, <http://www.clinicaltrials.gov>. All results of primary and secondary objectives must be posted to CT.gov within a year of completion. The sponsor-investigator has delegated responsibility to HCRN for registering the trial and posting the results on clinicaltrials.gov. Information posted will allow subjects to identify potentially appropriate trials for their disease conditions and pursue participation by calling a central contact number for further information on appropriate trial locations and study site contact information.

14. DATA HANDLING AND RECORD KEEPING

14.1 Data Management

HCRN will serve as the Clinical Research Organization for this trial. Data will be collected through a web-based clinical research platform, a system compliant with Good Clinical Practices and Federal Rules and Regulations. HCRN personnel will coordinate and manage data for quality control assurance and integrity. All data will be collected and entered into the EDC system by study site personnel from participating institutions.

14.2 Case Report Forms and Submission

Generally, clinical data will be electronically captured in the EDC system and correlative results will be captured in the EDC system or another secure database(s). If procedures on the study calendar are performed for standard of care, at minimum, that data will be captured in the source document. Select standard of care data will also be captured in the EDC system, according to study-specific objectives.

The completed dataset is the sole property of the sponsor-investigator's institution and should not be exported to third parties, except for authorized representatives of appropriate Health/Regulatory Authorities, without permission from the sponsor-investigator and HCRN.

14.3 Record Retention

To enable evaluations and/or audits from Health Authorities/HCRN, the site investigator agrees to keep records, including the identity of all subjects (sufficient information to link records; e.g., hospital records), all original signed informed consent forms, copies of all source documents, and detailed records of drug disposition. All source documents are to remain in the subject's file and retained by the site investigator in compliance with the site contract with HCRN. No records will be destroyed until HCRN confirms destruction is permitted.

14.4 Confidentiality

There is a slight risk of loss of confidentiality of subject information. All records identifying the subjects will be kept confidential and, to the extent permitted by the applicable laws and/or regulations, will not be made publicly available. Information collected will be maintained on secure, password protected electronic systems. Paper files that contain personal information will be kept in locked and secure locations only accessible to the study site personnel.

Subjects will be informed in writing that some organizations including the sponsor-investigator and his/her research associates, HCRN, Bavarian Nordic, BMS, IRB, or government agencies, like the FDA, may inspect their medical records to verify the information collected, and that all personal information made available for inspection will be handled in strictest confidence and in accordance with local data protection laws.

If the results of the study are published, the subject's identity will remain confidential.

15 ETHICS

15.1 Institutional Review Board (IRB) Approval

The final study protocol and the final version of the informed consent form must be approved in writing by an IRB. The site investigator must submit written approval by the IRB to HCRN before he or she can enroll subjects into the study.

The site investigator is responsible for informing the IRB of any amendment to the protocol in accordance with local requirements. In addition, the IRB must approve all advertising used to recruit subjects for the study. The protocol must be re-approved by the IRB, as local regulations require.

Progress reports and notifications of serious and unexpected adverse events will be provided to the IRB according to local regulations and guidelines.

15.2 Ethical Conduct of the Study

The study will be performed in accordance with ethical principles originating from the Declaration of Helsinki. Conduct of the study will be in compliance with ICH Good Clinical Practice, and with all applicable federal (including 21 CFR parts 56 & 50), state, or local laws.

15.3 Informed Consent Process

The site investigator will ensure the subject is given full and adequate oral and written information about the nature, purpose, possible risks and benefits of the study. Subjects must also be notified they are free to discontinue from the study at any time. The subject should be given the opportunity to ask questions and allowed time to consider the information provided.

The subject's signed and dated informed consent must be obtained before conducting any procedure specifically for the study. The site investigator must store the original, signed informed consent form. A copy of the signed informed consent form must be given to the subject.

APPENDIX 1: MANAGEMENT ALGORITHMS

GI Adverse Event Management Algorithm

[figure not shown]
Rule out non-inflammatory causes. If non-inflammatory cause is identified, treat accordingly and continue I-O therapy. Opiates/narcotics may mask symptoms of perforation. Infliximab should not be used in cases of perforation or sepsis.

Patients on IV steroids may be switched to an equivalent dose of oral corticosteroids (e.g. prednisone) at start of tapering or earlier, once sustained clinical improvement is observed. Lower bioavailability of oral corticosteroids should be taken into account when switching to the equivalent dose of oral corticosteroids.

Renal Adverse Event Management Algorithm

[figure not shown]
Rule out non-inflammatory causes. If non-inflammatory cause, treat accordingly and continue I-O therapy

Patients on IV steroids may be switched to an equivalent dose of oral corticosteroids (e.g. prednisone) at start of tapering or earlier, once sustained clinical improvement is observed. Lower bioavailability of oral corticosteroids should be taken into account when switching to the equivalent dose of oral corticosteroids.

Pulmonary Adverse Event Management Algorithm

[figure not shown]
Rule out non-inflammatory causes. If non-inflammatory cause, treat accordingly and continue I-O therapy. Evaluate with Imaging and pulmonary consultation.

Patients on IV steroids may be switched to an equivalent dose of oral corticosteroids (e.g. prednisone) at start of tapering or earlier, once sustained clinical improvement is observed. Lower bioavailability of oral corticosteroids should be taken into account when switching to the equivalent dose of oral corticosteroids.

Hepatic Adverse Event Management Algorithm

Rule out non-inflammatory causes. If non-inflammatory cause, treat accordingly and continue I-O therapy. Consider Imaging for obstruction.

[figure not shown]
Patients on IV steroids may be switched to an equivalent dose of oral corticosteroids (e.g. prednisone) at start of tapering or earlier, once sustained clinical improvement is observed. Lower bioavailability of oral corticosteroids should be taken into account when switching to the equivalent dose of oral corticosteroids.

*I-O therapy may be delayed rather than discontinued if AST/ALT ≤ 8 x ULN and T.bili ≤ 5 x ULN.

**The recommended starting dose for grade 4 hepatitis is 2 mg/kg/day methylprednisolone IV.

Endocrinopathy Management Algorithm

[figure not shown]
Rule out non-inflammatory causes. If non-inflammatory cause, treat accordingly and continue I-O therapy. Consider visual field testing, endocrinology consultation, and imaging.

Patients on IV steroids may be switched to an equivalent dose of oral corticosteroids (e.g. prednisone) at start of tapering or earlier, once sustained clinical improvement is observed. Lower bioavailability of oral corticosteroids should be taken into account when switching to the equivalent dose of oral corticosteroids.

Skin Adverse Event Management Algorithm

Rule out non-inflammatory causes. If non-inflammatory cause, treat accordingly and continue I-O therapy.

[figure not shown]

Patients on IV steroids may be switched to an equivalent dose of oral corticosteroids (e.g. prednisone) at start of tapering or earlier, once sustained clinical improvement is observed. Lower bioavailability of oral corticosteroids should be taken into account when switching to the equivalent dose of oral corticosteroids.

*Refer to NCI CTCAE v4 for term-specific grading criteria.

[figure not shown]
Neurological Adverse Event Management Algorithm

Rule out non-inflammatory causes. If non-inflammatory cause, treat accordingly and continue I-O therapy.

Patients on IV steroids may be switched to an equivalent dose of oral corticosteroids (e.g. prednisone) at start of tapering or earlier, once sustained clinical improvement is observed. Lower bioavailability of oral corticosteroids should be taken into account when switching to the equivalent dose of oral corticosteroids.

Myocarditis Adverse Event Management Algorithm

Patients on IV steroids may be switched to an equivalent dose of oral corticosteroids (eg, prednisone) at start of tapering or earlier, once sustained clinical improvement is observed. Lower bioavailability of oral corticosteroids should be taken into account when switching to the equivalent dose of oral corticosteroids.

Prophylactic antibiotics should be considered in the setting of ongoing immunosuppression.

ATG = anti-thymocyte globulin; BNP = B-type natriuretic peptide; ECG = electrocardiogram; IV = intravenous; MRI = magnetic resonance imaging

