6.3 Nivolumab

There will be no dose escalations or reductions of nivolumab allowed. Premedications are not recommended for the first dose of nivolumab. Participants should be carefully monitored for infusion reactions during nivolumab administration. Doses of nivolumab may be interrupted, delayed, or discontinued depending on how well the participant tolerates the treatment. Guidelines on the recommended management are provided in the Investigator Brochure.

Nivolumab administration should be delayed for the following:

- Given hepatic involvement as an inclusion criteria, continue, withhold or permanently discontinue nivolumab based on the severity of hepatitis and baseline AST and ALT levels (following guidelines for use of nivolumab in HCC liver disease):
 - If AST/ALT is within normal limits at baseline and increases to > 3-5x the ULN, withhold dose
 - If AST/ALT is > 1-3x ULN at baseline and increases to > 5-8x the ULN, withhold dose
 - If AST/ALT is > 3-5x ULN at baseline and increases to > 8x the ULN, withhold dose
- Grade 2 non-skin, drug-related AE, with the exception of fatigue
- Grade 2 drug-related creatinine abnormalities
- Grade 3 skin, drug-related AE
- Grade 3 drug-related laboratory abnormality, with the following exceptions:
 - Grade 3 lymphopenia or asymptomatic amylase or lipase does not require dose delay

- Any adverse event, laboratory abnormality, or intercurrent illness which, in the judgment of the investigator, warrants delaying the dose of study medication.

Participants who require delay of nivolumab should be re-evaluated weekly or more frequently if clinically indicated and resume nivolumab dosing when re-treatment criteria are met. In general, in the event of a grade 2 AE, treatment with nivolumab can be resumed when the AE has resolved to \leq grade 1.

Nivolumab treatment should be permanently discontinued for the following:

- If AST/ALT increases to $> 10x$ the ULN or total bilirubin increases to $> 3x$ ULN, permanently discontinue (following guidelines for use of nivolumab in HCC liver disease).
- Any Grade 2 drug-related uveitis, eye pain or blurred vision that does not respond to topical therapy and does not improve to Grade 1 severity within the re-treatment period OR requires systemic treatment

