- Any Grade 3 non-skin, drug-related AE lasting > 7 days or recurs, with the following exceptions for laboratory abnormalities, drug-related uveitis, pneumonitis, bronchospasm, neurologic toxicity, hypersensitivity reactions, infusion reactions, and endocrinopathies:
 - Grade 3 drug-related uveitis, pneumonitis, bronchospasm, neurologic toxicity, hypersensitivity reaction, or infusion reaction of any duration requires discontinuation
 - Grade 3 drug-related endocrinopathies, adequately controlled with only physiologic hormone replacement do not require discontinuation. Adrenal insufficiency requires discontinuation regardless of control with hormone replacement.
 - Grade 3 drug-related laboratory abnormalities do not require treatment discontinuation except:
 - Grade 3 drug-related thrombocytopenia > 7 days or associated with bleeding requires discontinuation

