6.3.12 Criteria to Resume Nivolumab Dosing

Participants may resume treatment with study treatment when the drug-related AE(s) resolve to Grade \leq 1 or baseline value, with the following exceptions:

- Participants may resume treatment in the presence of Grade 2 fatigue
- Participants who have not experienced a Grade 3 drug-related skin AE may resume treatment in the presence of Grade 2 skin toxicity
- For participants with Grade 2 AST, ALT and/or Total Bilirubin Abnormalities, dosing may resume when laboratory values return to baseline and management with corticosteroids, if needed, is complete.
- Drug-related pulmonary toxicity, diarrhea or colitis must have resolved to baseline before treatment is resumed. Participants with persistent Grade 1 pneumonitis after completion of a steroid taper over at least 1 month may be eligible for retreatment if discussed with and approved by the site sponsor-investigator

Participants with drug-related endocrinopathies adequately controlled with only physiologic hormone replacement may resume treatment after consultation with the sponsor-investigator. Adrenal insufficiency requires discontinuation regardless of control with hormone replacement.

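### For total bilirubin above 3x and up to 5x ULN with AST/ALT at or below 8x ULN, Section 6.3 stops nivolumab for good while the Appendix 1 hepatic footnote allows delay, and the visible text does not rank them

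*Combined protocol and SAP*

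**What the plan says.** Section 6.3 (Nivolumab) sets the hepatic limits for this trial and explains why they are adapted: "Given hepatic involvement as an inclusion criteria, continue, withhold or permanently discontinue nivolumab", according to how severe the hepatitis is and the baseline transaminases. The section then lists reasons for permanent discontinuation. One bullet names AST/ALT above 10x ULN or, as an alternative, bilirubin: "total bilirubin increases to $> 3x$ ULN, permanently discontinue". The list is introduced with *should*.

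The hepatic algorithm in Appendix 1 carries a footnote addressed to immuno-oncology therapy in general: "I-O therapy may be delayed rather than discontinued if AST/ALT ≤ 8 x ULN and T.bili ≤ 5 x ULN". Nivolumab is a PD-1 blocking antibody (Section 5), so the footnote covers it.

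Section 6.3.12 governs resumption after a delay. The general rule reads "Participants may resume treatment with study treatment when the drug-related AE(s) resolve to Grade" 1 or lower, or to the baseline value. A liver-specific exception follows: "For participants with Grade 2 AST, ALT and/or Total Bilirubin Abnormalities, dosing may resume when laboratory values return to baseline", with any corticosteroid course finished. Section 6.3.11 also allows nivolumab to restart after a steroid taper once an immune-related reaction has improved.

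For management guidance Section 6.3 refers to the Investigator Brochure. It does not mention Appendix 1 or say which text prevails.

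**The concern.** A permanent-stop rule for liver toxicity should give one answer for one patient. Here a patient with bilirubin at 4x ULN and AST/ALT at 6x ULN is to come off nivolumab for good under Section 6.3, yet may be held and later re-treated under Appendix 1. Two sites could handle identical patients differently, and the site that delays could point to the protocol's own appendix in support.

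What is at stake is re-exposure to a checkpoint inhibitor after a bilirubin rise that the liver-adapted rule treats as disqualifying. The population makes the rule relevant: all patients have liver metastases, most are expected to have a liver resection, and nivolumab can continue through Cycle 36.

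**Working it through.** No sample size, power or event count is involved. The check is a comparison of two threshold rules, in multiples of ULN.

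**Inputs**
- Rule A (Section 6.3): stop permanently if bilirubin > 3 **or** AST/ALT > 10.
- Rule B (Appendix 1 hepatic footnote): delay permitted if bilirubin ≤ 5 **and** AST/ALT ≤ 8.
- Entry limit (Section 3.1, organ function table): bilirubin ≤ 1.5, or < 2 for isolated congenital hyperbilirubinemia.
- Potential drug-induced liver injury, handled as an SAE (Section 11.1.2): AST/ALT > 3 and bilirubin > 2, with no cholestasis and no other apparent cause.

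**Step 1: where both rules apply.** If AST/ALT ≤ 8, the AST/ALT arm of Rule A (> 10) cannot be met, so any overlap comes from the bilirubin arm alone. Both rules then hold when 3 < bilirubin ≤ 5 and AST/ALT ≤ 8. The band is 5 − 3 = 2 multiples of ULN wide.

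**Step 2: test cases**

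| Bilirubin | AST/ALT | Section 6.3 | Footnote | Conflict |
|---|---|---|---|---|
| 3.0 | 8 | no permanent stop | delay permitted | no |
| 3.1 | 8 | permanent stop | delay permitted | yes |
| 4.0 | 6 | permanent stop | delay permitted | yes |
| 5.0 | 8 | permanent stop | delay permitted | yes |
| 3.1 | 2.9 | permanent stop | delay permitted | yes |
| 5.1 | 8 | permanent stop | does not apply | no |
| 3.1 | 8.1 | permanent stop | does not apply | no |

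**Step 3: does the difference matter in practice?** Permanent discontinuation closes the route back to nivolumab. Delay keeps it open under Sections 6.3.11 and 6.3.12. The documents do not state the CTCAE grade of a bilirubin of 3x to 5x ULN, so they do not settle whether the general resumption rule or the Grade 2 liver exception would apply. Under either, resumption is possible.

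**Step 4: how far a patient must move to get there.** From the entry cap the rise must exceed 3 / 1.5 = 2-fold. From just under 2x it must exceed about 3 / 2 = 1.5-fold. The documents do not say how often this happens.

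**Step 5: what the SAE rule reaches.** Within the conflict zone, AST/ALT above 3x and up to 8x meets the laboratory part of the liver-injury definition. AST/ALT at or below 3x does not.

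**The case against.** The strongest reply is that an ordinary reading already favours Section 6.3. It is specific to this trial and to nivolumab and is expressly adapted to liver involvement, while the appendix speaks generically. The footnote only says *may*, so a site that discontinues breaks neither text. Part of this stands: it points to which limit was probably intended. But the site has to infer it, and a site that delays is following an instruction printed in the protocol.

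A second reply is that a delayed patient is not simply re-treated. Section 6.3 asks for re-evaluation at least weekly during a delay. Section 6.3.3 asks for liver tests before each nivolumab dose and for consultation with the sponsor-investigator on all moderate- and high-grade hepatic events, whatever the AST/ALT level. Potential liver injury goes through SAE review (Sections 11.1.2 and 11.3), and the monitoring committee meets quarterly (Section 13.2). These are real safeguards and they lower the weight of the point. None of them names the governing limit, and the sponsor-investigator who is consulted faces the same two numbers.

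A third reply is that the algorithm figure is not shown and the Investigator Brochure is not among the documents; either might settle the matter. That stands as a limit on certainty. The footnote does state its own thresholds and action in words, so the conflict is present on the face of the text.

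Three stronger readings are tempting and are not supported:
- A reader might infer the opposite mismatch at AST/ALT above 8x and up to 10x, because Section 6.3 says "If AST/ALT is > 3-5x ULN at baseline and increases to > 8x the ULN, withhold dose" and stops permanently only above 10x. But a footnote that withholds permission to delay is not an instruction to discontinue, and the branch that it qualifies cannot be seen.
- A reader might infer that the rule "Grade 3 drug-related laboratory abnormalities do not require treatment discontinuation except" (the listed exception concerns thrombocytopenia) overrides the bilirubin bullet. That needs the CTCAE grade, which the documents do not give, and a specific bullet need not yield to a general exception.
- A reader might infer a further conflict from the algorithm's line "If non-inflammatory cause, treat accordingly and continue I-O therapy. Consider Imaging for obstruction". Without the figure it cannot be shown that this line and the bilirubin limit address the same situation.

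**Conclusion.** The inconsistency holds on the visible text for total bilirubin above 3x and up to 5x ULN with AST/ALT at or below 8x ULN, and nowhere else that the documents can establish. It is a minor-to-moderate patient-safety matter of unknown frequency. A reader might say that the protocol commands a stop and that the footnote breaches it; the documents do not go that far, since Section 6.3 uses *should* and the footnote uses *may*.

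The same hepatic rules apply to nivolumab in both arms, so there is no consequence for between-arm bias, alpha or power. The conclusion assumes that neither the unseen figure nor other text not available here contains a precedence statement.

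**What to change.** In the Appendix 1 hepatic footnote, change the bilirubin limit from 5x to 3x ULN, and add one sentence:

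*For nivolumab in this trial, the Section 6.3 AST/ALT and total bilirubin withhold and discontinuation limits govern over any differing AST/ALT or bilirubin threshold in the Appendix 1 hepatic algorithm.*

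With the new limit, the overlap would need bilirubin both > 3 and ≤ 3, so the conflict zone is empty. The sentence is still needed: the footnote would keep its 8x AST/ALT figure beside the 10x stop in Section 6.3, and the figure may contain other thresholds.

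If the clinical team in fact intends 5x, the Section 6.3 bullet should be amended instead, so that one number remains.

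The cost is a footnote edit, one sentence and a letter to sites, with no added procedures or data. The clinical downside is that a few patients who could have been delayed under the footnote will stop nivolumab permanently.
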